20. Has received a live vaccine within 30 days of planned start of trial therapy.

Note: Seasonal influenza vaccines for injection are generally inactivated flu vaccines and are allowed; however intranasal influenza vaccines (e.g., Flu-Mist®) are live attenuated vaccines, and are not allowed.

Statistical Methods: The primary endpoint for this clinical trial is the percent of patients with radiographic disease progression according to RECIST 1.1 at 6 months. Without maintenance therapy, 92% of patients are expected to progress by 6 months. Therefore, we assume 1/12 (0.083) pembrolizumab + placebo arm show no progression versus 7/12 pembrolizumab + paricalcitol. This gives 90% statistical power with one side alpha = (0.05).

Statistical analysis will compare the proportion progression free at 6 months using a one-sided test comparing binomial proportions (equivalent to a Pearson's chi-square test). The incidence of toxicities will be tabulated. Overall survival will be estimated for each arm using a Kaplan-Meier estimate. Statistical comparison of overall survival will be performed using a log-rank test with estimation of the hazards ratio using a Cox proportional hazards model.

TABLE OF CONTENTS

| | |
|---|----|
| 1.0 BACKGROUND AND RATIONALE | 24 |
| 1.1 Overview | 24 |
| 1.2 A major developing problem in the care of patients with advanced pancreatic cancer | 24 |
| 1.3 Rationale - The reasoning behind a maintenance regimen | 25 |
| 1.4 Pembrolizumab (Keytruda®) | 26 |
| 1.5 Paricalcitol (Zemlar®) | 29 |
| 1.6 Trial Dose Rationale and Sequence | 30 |
| 1.6.1 Pembrolizumab Dose | 30 |
| 1.6.2 Paricalcitol Dose | 31 |
| 2.0 HYPOTHESIS..... | 32 |
| 3.0 OBJECTIVES | 32 |
| 3.1 Primary Objective | 32 |
| 3.2 Secondary Objectives..... | 32 |
| 3.3 Exploratory Objectives..... | 32 |
| 3.4 Primary Endpoints | 33 |
| 3.5 Secondary Endpoints | 33 |
| 3.6 Exploratory Endpoints | 33 |
| 4.0 METHODS..... | 33 |
| 4.1 Eligibility | 33 |
| 4.1.1 Inclusion Criteria | 34 |
| 4.1.2 Exclusion Criteria | 35 |
| 4.2 Trial Treatments | 37 |
| 4.2.1 Dose Selection/Modification | 37 |
| 4.2.2 Paricalcitol (Zemlar®) and Placebo | 38 |
| 4.2.3 Pembrolizumab (Keytruda®)..... | 38 |
| 4.2.4 Dose Modification (Escalation/Titration/Other) of Pembrolizumab (Keytruda®) in cases of Toxicity..... | 39 |
| 4.2.5 Dose Interruption of Paricalcitol in Cases of Toxicity | 44 |
| 4.2.6 Timing of Dose Administration..... | 44 |
| 4.2.7 Trial Blinding/Masking | 45 |

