4.3 Randomization or Treatment Allocation

Randomization will be in a 1:1 ratio to pembrolizumab + paricalcitol or pembrolizumab + placebo. Randomization will be performed by the trial biostatistician or designee using a computer-generated algorithm with a block size of 4. The RAND function in MySQL is used to generate a random number, with a value based on the computer clock used as seed. The program randomly assigns participants to one of the two treatments with the pre-selected block size. After study initiation, the randomization sequence will be provided to the unblinded central monitor. After consent and confirmation of eligibility, the site study coordinator will notify the site pharmacist and the unblinded monitor. The unblinded monitor will provide the next randomized treatment from the sequence to the site pharmacist. The unblinded monitor also will notify the trial biostatistician. The trial biostatistician or designee will be available to assist with identifying the next randomized treatment if the unblinded central monitor is not available.

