8.2 Sample Size Considerations

The primary endpoint is the percentage of patients progressing at 6 months. Based on a contemporary control of no maintenance after best response to prior chemotherapy⁸, the control arm with pembrolizumab alone is expected to have only 8% of patients with no progression at 6 months. To be of clinical interest, at least 58% of patients must be progression-free at 6 months on the pembrolizumab plus paricalcitol arm. A sample size of 12 patients per arm will provide 90% statistical power to detect this difference assuming a one-sided alpha level of 0.05. A one-sided test was selected as we are only interested in the combination if it decreases the percentage of patients progressing at 6 months. This sample size estimate was obtained using binomial enumeration of all possible outcomes to compare two independent binomial proportions (Pearson's chi-squared test) using PASS 15.¹⁸ A statistical concern is that the Pearson chi-squared test does not guarantee the alpha level. We confirmed that we have adequate statistical power using the Miettinen & Nurminen¹⁹ exact likelihood score method (89% power) using Pass 15.

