3 ANALYSIS OBJECTIVES

The primary objective is to determine whether combined paricalcitol + pembrolizumab reduces disease progression compared to pembrolizumab alone among patients with stage IV pancreatic cancer who have been put in best response.

The primary endpoint is the percent of patients with radiographic disease progression according to RECIST 1.1 at 6 months.

Secondary objectives include:

- (1) Evaluate the toxicity of the combination of paricalcitol + pembrolizumab versus pembrolizumab alone.
- (2) Evaluate the difference in overall survival in patients administered the combination of paricalcitol + pembrolizumab versus pembrolizumab alone.

Exploratory objectives include:

- (1) Evaluate the difference in disease progression according to iRECIST vs. RECIST 1.1 criteria.

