4 ANALYSIS SETS/ POPULATIONS/ SUBGROUPS

This trial will have 24 patients randomized to paricalcitol + pembrolizumab (n=12) or pembrolizumab alone (n=12). No stratification will be performed.

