7 STATISTICAL METHODOLOGY

7.1 STATISTICAL PROCEDURES

Primary outcome: Progression-free survival

The proportion of patients in each arm who are progression-free at 6-months will be compared using a one-sided test of binomial proportions (equivalent to a Pearson's chi-squared test). If the assumptions of the Pearson's chi-squared test are not met, Barnard's exact unconditional test of equality will be used, as implemented in StatXact.

Patients unevaluable for progression at 6-months due to a non-progression related event will be excluded from analysis.

Statistical comparison of progression-free survival between the two treatment arms will be performed using a log-rank test, with estimation of the hazards ratio using a Cox proportional hazards model. A sensitivity analysis will include patients with an outcome of death due to another cause (other than progressive disease), which will be considered a competing event for progression. Analysis will be performed using the Fine and Gray (1999) approach.

Secondary outcome 1: Toxicity

All adverse events (AE) occurring on or after C1/D1 will be summarized by body systems and per grade according to NCI-CTCAE Version 4. Additionally, all serious adverse events (SAE) and events of clinical interest (ECI) will be listed separately and tabulated. ECIs for this trial include an overdose of pembrolizumab and an elevated AST or ALT lab value, as defined in section 6.2.3.2 of the protocol. All patients who receive any amount of trial treatment will be included in the analysis. The proportion of patients in each arm with toxicity will be compared using a chi-squared test or Barnard's exact unconditional test of equality as outlined above.

Secondary outcome 2: Overall survival

Overall survival will be calculated for each arm using a Kaplan-Meier estimate. Statistical comparison of overall survival between the two treatment arms will be performed using a log-rank test, with estimation of the hazards ratio using a Cox proportional hazards model. Patients with an outcome of death due to another cause (other than progressive disease) will be considered a competing event for death. Analysis will be performed using the Fine and Gray (1999) approach.

Exploratory outcome 1: RECIST 1.1 versus iRECIST

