Rate of progression-free survival, % (95% CI)				
6 mo				
12 mo				
Median progression-free survival, mo (95% CI)				
Overall survival				
Median overall survival, mo (95% CI)				
Survival rate, % (95% CI)				
6 mo				
12 mo				

Table 3. Common adverse events of grade 3 or higher

Event	Pembrolizumab n = x	Pembrolizumab + Paricalcitol n = x	P value
Adverse event leading to death, no. (%)			
Serious Adverse Events			
Anemia			
Cataract			
Nausea			
Abdominal pain			
Diarrhea			
Vomiting			
Bloating			
Constipation			
Fatigue			
Gait disturbance			
Urinary tract infection			
AST increased			
ALT increased			
Alkaline phosphatase increased			
Arthralgia			
Pain in extremity			
Back pain			
Hypertension			

Note: these were the most common events on the Nov 2019 DSMB report (> 10% of patients)

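### The only inferential between-arm output for toxicity is a p-value beside per-arm counts, with no risk difference or confidence interval, at a sample size where a non-significant result says little

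*SAP*

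**What the plan says.** SAP 3 lists as its first secondary objective: "Evaluate the toxicity of the combination of paricalcitol + pembrolizumab versus pembrolizumab alone". Protocol 3.2 has the same objective.

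SAP 7.1, under toxicity, plans summaries of adverse events by body system and grade, and separate listings and tabulations of serious adverse events and events of clinical interest. All treated patients are included. It then adds the comparison: "The proportion of patients in each arm with toxicity will be compared using a chi-squared test or Barnard's exact unconditional test of equality". That sentence ends by referring back to the method given for the primary outcome, which is a one-sided test. No alpha level, side or direction is given for toxicity itself, and the text does not say whether toxicity means any event, a severe event or a related event.

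The table shell for severe events, "Common adverse events of grade 3 or higher" (SAP Table 3), has a column for each arm and a P value column. Its first row is laid out as number and percentage. It has no column for a difference, ratio or interval, and no row for patients with at least one event of grade 3 or higher. SAP Table 2, for efficacy, has a column for a ratio with its 95% CI as well as a p-value. Protocol 8.3.5.1 plans tabulation only.

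The only power statement is for the primary endpoint (Protocol 8.2): "A sample size of 12 patients per arm will provide 90% statistical power to detect this difference assuming a one-sided alpha level of 0.05".

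**The concern.** A comparative objective needs an estimate of how much toxicity paricalcitol adds and how uncertain that estimate is. A test of equality gives neither. With 12 patients per arm, failing to reject is the most likely result even when the true excess is 20 points, so the p-value hardly separates no added harm from a relevant excess.

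A reader of Table 3 can subtract one percentage from the other but sees no statement of uncertainty. A column of large p-values beside small counts is easily read as similar toxicity. That reading could enter the decision on whether to take the combination further.

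**Working it through.** **Inputs.** 12 patients per arm (SAP 4; Protocol 8.2), randomised 1:1 (Protocol 4.3). Patients randomised but never treated are replaced (Protocol 4.9), so about 12 treated per arm. Toxicity rates are not in the documents; control rates of 10-25% are assumed below. Alpha 0.05 is also assumed, with both sides shown because the SAP does not state one.

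**Method.** All 13 × 13 possible tables are enumerated under independent binomials. For x events in control and y in combination, the Pearson statistic is z = (y/12 − x/12) / √[p(1 − p)(2/12)], with p = (x + y)/24. The Barnard p-value is the largest null probability, over the common event rate, of a z at least as extreme. Miss rate = 1 − probability of rejecting in the direction of harm.

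**Check on the plan's own figure.** For the primary endpoint the synopsis states: "we assume 1/12 (0.083) pembrolizumab + placebo arm show no progression versus 7/12 pembrolizumab + paricalcitol". Enumeration with one-sided Pearson at 0.05 gives 90.1% power (90.3% at 8% v 58%), against the stated 90%. The Miettinen-Nurminen statistic gives 88.8% to 89.1%, against the stated "exact likelihood score method (89% power) using Pass 15". The method therefore reproduces the plan.

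**Miss rates for toxicity at 12 v 12.**

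| Control v combination | Excess | Two-sided, Pearson / Barnard | One-sided, Pearson / Barnard |
|---|---|---|---|
| 10% v 30% | 20 points | 80% / 80% | 65% / 68% |
| 20% v 40% | 20 points | 82% / 83% | 69% / 76% |
| 25% v 45% | 20 points | 82% / 84% | 69% / 78% |
| 10% v 40% | 30 points | 61% / 62% | 44% / 49% |
| 20% v 50% | 30 points | 64% / 68% | 49% / 60% |
| 25% v 55% | 30 points | 64% / 71% | 51% / 62% |
| 10% v 50% | 40 points | 40% / 41% | 24% / 31% |

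For control rates of 10-30%, 80% power needs an excess of about 51-57 points two-sided, or 43-52 points one-sided.

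**What an interval would show.** Newcombe's interval combines the Wilson limits (l, u) of each arm. With control proportion p1, combination proportion p2 and d = p2 − p1:

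lower = d − √[(p2 − l2)² + (u1 − p1)²]; upper = d + √[(u2 − p2)² + (p1 − l1)²].

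- 1/12 v 4/12: Wilson limits are 0.015 to 0.354 and 0.138 to 0.609, and d = 0.250. Lower = 0.250 − √(0.0381 + 0.0732) = −0.084. Upper = 0.250 + √(0.0762 + 0.0047) = 0.534. The difference is +25 points (−8 to +53); two-sided Barnard p = 0.16.
- 3/12 v 3/12: Wilson limits are 0.089 to 0.532 in each arm, and d = 0. Half-width = √(0.0259 + 0.0797) = 0.325. The difference is 0 (−33 to +33).

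Even identical counts leave an excess of about 33 points compatible with the data. A p-value alone does not show this.

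**The case against.** The strongest reply is that low power for adverse events is inherent in a 24-patient phase II trial sized on progression, and that no SAP wording changes it. That is true. But the point asks for no more patients, only that the uncertainty be shown, as Table 2 already does for efficacy.

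The documents do not support several stronger readings that a reader might infer:

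- *The p-value is the only between-arm safety information.* It is not. Per-arm columns, summaries by grade, and SAE and ECI tabulations are planned, so a crude difference can be read off. Protocol 9.8.2 also provides an unblinded report to the independent medical monitor, with content not specified. What is missing is a stated difference with an interval.
- *The test will nearly always be non-significant, whatever the harm.* At 10% v 50%, a two-sided test misses the excess in only about 40% of trials.
- *Any non-significant row is compatible with an excess above 50 points.* This depends on the counts. The Newcombe upper limit is +24 for 0/12 v 0/12, +33 for 3/12 v 3/12 and +46 for 1/12 v 3/12. By enumeration (Pearson, two-sided) it exceeds +50 in about 4%, 17% and 35% of non-significant trials when the true rates are 10% v 10%, 10% v 20% and 10% v 30%.
- *The plan declares the combination safe if p exceeds 0.05.* No such rule is written. The risk is one of interpretation.

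The reply is also right that the two-sided figures are conditional. SAP 7.1 can be read as importing the one-sided test, under which the miss rates are lower, though still substantial.

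**Conclusion.** The concern holds as a gap in the planned comparison. For the first secondary objective, the only inferential output is a p-value, with no effect estimate or interval. At 12 per arm and assumed control rates of 10-20%, a two-sided 0.05 test misses a 20-point excess in about 80-83% of trials and a 30-point excess in about 61-68% (Pearson and Barnard together). Under a one-sided 0.05 reading, the Pearson figures are about 65-69% and 44-49%, and Barnard's are higher. Moving the control rate to 25% raises the upper ends slightly, as the table above shows.

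The sizes rest on assumed event rates, an assumed alpha of 0.05, and a side that the SAP does not state. Reading toxicity as severe toxicity rests on the Table 3 title, not on the text of SAP 7.1. The absence of any planned interval depends on none of these. The change is worth making because it is cheap and bears directly on a stated objective; it does not touch the primary analysis.

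**What to change.** In SAP 7.1 and Table 3:

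1. Add the risk difference (combination minus control) with a 95% CI, by Newcombe's method or an exact unconditional method, for each row.
2. Add a row for patients with any event of grade 3 or higher, with the same estimate and interval.
3. Name this the main between-arm safety comparison. P-values may stay as secondary information, with their side and level stated.
4. State that a non-significant test is not evidence of similar toxicity.

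The cost is a few sentences of SAP text, one table column and one row, from data already collected. The downside is that the intervals will be wide and the safety statement less reassuring.

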- r. For only those patients consenting to the optional tumor biopsy, a baseline tumor biopsy will be collected and used for profiling. If possible (patient condition permitting) this will be repeated after 9 ± 1 weeks on trial treatment, or at the time of disease progression. (Refer to 6.1.2.8).

Table 8. Post-Treatment Period (EOT– Follow-Up) Schedule

| Post-Treatment Period | Scheduling Window (Days) | | |
|--|--|----------------------|---|
| | EOT | 30 days from EOT | Every 90 days post EOT |
| | At time of discontinuation (within 5 days of last dose) | 30 ± 5 days from EOT | 90 ± 5 days from EOT then every 90 ± 15 days ⁱ |
| Post-trial anticancer treatment status | X | X | X |
| Disease/Survival Status ^a | X | X | X |
| Concomitant Medication Review | X | X | X |
| Assess & Report Adverse Events ^b | X | X | X |
| Directed Physical Examination | X | | |
| Patient Personalized Clinical Benefit App | X | | |
| Vital Signs and Weight ^c | X | | |
| ECG | X | | |
| ECOG (see appendix 4) | X | | |
| Serum β HCG Pregnancy Test for WOCBP | X | X | |
| CBC with Differential | X | | |
| Comprehensive Serum Chemistry Panel | X | | |
| Urinalysis | X | | |
| T3, FT4 and TSH | X | | |
| Tumor Imaging ^d | X | | |
| CA19-9 ^e | X | | |
| Central Lab Samples (Blood and Fecal Swab ^f) | X | X ^f | |
| Review contraception use as required by protocol Section 4.7.2 (where applicable) ^g | X | X | X |
| Optional -Tumor Tissue Collection | [Tumor tissue collection for those that consent to this optional collection and undergo a routine care biopsy of their tumor during their participation in the study] ^j | | |
| Contact Information Review ^h | X | X | X |

Footnotes for Table 8. Post –Treatment Period

a. Post-treatment follow-up for disease status until documented disease progression, initiating a non-trial cancer treatment, withdrawing consent or becoming lost to follow-up. After documented disease progression each pt will be followed by telephone for survival status.

b. Assess and record any new or ongoing AEs at time of EOT. Following the EOT, each patient will be followed for 30 days, for adverse event monitoring. Serious adverse events and Events of Clinical Interest (ECI) will be collected for 90 days after the end of treatment as described in Section 6.2.3.1.

c. Vital signs to include: Blood pressure, pulse, respiratory rate, and temperature.

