For the time period beginning at treatment allocation/randomization through 90 days following cessation of treatment, or 30 days following cessation of treatment if the patient initiates new anticancer therapy, whichever is earlier, any serious adverse event, or follow up to a serious adverse event, including death due to any cause other than progression of the cancer under study (reference Section 6.2.3.3 for additional details), whether or not related to the trial treatment, must be reported within 24 hours to the Sponsor. The Sponsor will report within 24 hours (working days) to Merck Global Safety.

Additionally, any serious adverse event, considered by an investigator who is a qualified physician to be related to pembrolizumab that is brought to the attention of the investigator at any time following consent through the end of the specified safety follow-up period specified in the paragraph above, or at any time outside of the time period specified in the previous paragraph also must be reported immediately to the Sponsor. The Sponsor will then report to Merck Global Safety.

All patients with serious adverse events must be followed up for outcome.

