8.3.5.2 Comparison of Overall Survival

Duration of survival will be defined as the time from initial treatment (cycle1/day1) until death. Overall survival will be estimated for each arm using a Kaplan-Meier estimate. Statistical comparison of overall survival between the two treatment arms will be performed using a log-rank test, with estimation of the hazards ratio using a Cox proportional hazards model.

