5 ENDPOINTS AND COVARIATES

Primary endpoint: Percent of patients with radiographic disease progression according to RECIST 1.1 at 6 months, defined as 180 days from initial treatment (C1/D1).

Secondary endpoints:

- (1) Incidence of toxicities
From initial treatment to end-of-treatment
- (2) Overall survival
Time from initial treatment to death

Exploratory endpoints:

- (1) Disease progression according to RECIST 1.1 versus iRECIST criteria
Percent of patients with radiographic disease progression at 6 months

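### SAP 7.1 lets a non-progression death compete with death under overall survival, so its Fine-Gray model can only describe progression-related death

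*SAP*

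**What the plan says.** Protocol 8.3.5.2 sets the endpoint: "Duration of survival will be defined as the time from initial treatment (cycle1/day1) until death". SAP section 5 agrees: "Time from initial treatment to death". Neither restricts the cause of death.

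The protocol plans three methods for overall survival: Kaplan-Meier, log-rank and Cox. The synopsis says "Statistical comparison of overall survival will be performed using a log-rank test", with the hazard ratio from a Cox model, and 8.3.5.2 repeats this. Neither place has a competing-risk analysis.

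SAP 7.1 keeps all three methods and then adds: "Patients with an outcome of death due to another cause (other than progressive disease) will be considered a competing event for death". A further sentence applies the Fine and Gray approach.

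The progression-free survival paragraph of SAP 7.1 has a close parallel: "A sensitivity analysis will include patients with an outcome of death due to another cause (other than progressive disease"). There the competing event is set against progression, not against death.

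**The concern.** A competing event is one that prevents the event of interest. Death from another cause can prevent progression, so the progression-free survival text is coherent. It cannot prevent death, because it is a death. With the endpoint defined as death from any cause, SAP 7.1 makes one death both the event and its competitor.

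A Fine-Gray model fitted as described would have to treat only deaths due to progressive disease as events. It would keep patients who died of other causes in the risk set, where they can no longer have the event. An arm with more non-progression deaths then looks better on this model and worse on all-cause survival. At stake is a hazard ratio produced under the overall survival heading that does not measure overall survival and can point the other way.

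**Working it through.** **1. The definitions side by side.** By protocol 8.3.5.2 and SAP 5, a non-progression death is an event. By the competing-event sentence in SAP 7.1, it is a competitor. Both hold only if the event in the Fine-Gray model is narrowed to progression-related death. The SAP does not state that narrowing; it is an inference, but no other reading is coherent.

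**2. Inputs for the size.** The documents give no power, event count, hazard ratio or cause-specific death rate for overall survival, so there is no stated figure to reproduce. The sample size, 12 per arm, is theirs. The rest is assumed: constant hazards, progression-death hazard p = 0.10 per month in both arms, non-progression hazard h1 (combination) and h0 = 0.005 (control), 24 months of follow-up, and administrative censoring only.

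**3. Formulas.**
- All-cause HR = (p + h1)/(p + h0). For h1 = 0.01: 0.11/0.105 = 1.048.
- Fine-Gray risk-set fraction in an arm: Y(t) = 1 − p/(p + h) × (1 − exp(−(p + h)t)). Progression-death density: f(t) = p × exp(−(p + h)t).
- The large-sample subdistribution HR is the θ that solves ∫ [f1 − (f1 + f0) × θY1/(Y0 + θY1)] dt = 0 over 0 to 24 months.
- Expected non-progression deaths among 12 = 12 × h/(p + h) × (1 − exp(−24(p + h))). For h = 0.01: 12 × 0.0909 × 0.9286 = 1.01. For h = 0.005: 12 × 0.0476 × 0.9195 = 0.53.

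**4. Results.** The last two columns come from 40,000 simulated trials of 12 per arm. Opposite means all-cause HR above 1 with subdistribution HR below 1. The final column adds a nominally significant Fine-Gray result (two-sided 0.05).

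| h1 vs h0 | All-cause HR | Subdistribution HR | Opposite | Opposite and significant |
|---|---|---|---|---|
| 0.005 vs 0.005 | 1.00 | 1.00 | 7.5% | 0.0% |
| 0.01 vs 0.005 | 1.05 | 0.93 | 15.3% | 0.03% |
| 0.02 vs 0.005 | 1.14 | 0.83 | 30.2% | 0.4% |
| 0.03 vs 0.005 | 1.24 | 0.75 | 43.3% | about 1.4% |

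With 12 months of follow-up the last three subdistribution HRs are 0.97, 0.91 and 0.85, with the same all-cause HRs. Reversing the imbalance (0.005 vs 0.02) gives 1.21 against an all-cause HR of 0.875, so the error can run either way.

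**5. Precision.** For 0.01 vs 0.005 the central 95% of simulated estimates runs from 0.36 to 2.41 (subdistribution) and from 0.41 to 2.69 (all-cause). About 20% of such trials have no non-progression death, and the two analyses then coincide.

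**6. When it does no harm.** With equal non-progression hazards of 0.01, and progression-death hazards of 0.06 against 0.09, the all-cause HR is 0.70 and the subdistribution HR is 0.69. The gap depends on imbalance in non-progression deaths.

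**7. Cause of death.** The model needs a cause for each death.
- Serious adverse events, including deaths not due to progression, are reportable "through 90 days following cessation of treatment, or 30 days following cessation of treatment if the patient initiates new anticancer therapy, whichever is earlier" (protocol 6.2.3.1). Pembrolizumab-related serious events that come to notice "at any time outside of the time period specified in the previous paragraph also must be reported immediately to the Sponsor".
- Patients who stop treatment without progression have disease-status follow-up every 90 days (protocol 4.8, 4.9 and Table 8).
- After progression, Table 8 footnote a says: "After documented disease progression each pt will be followed by telephone for survival status". Protocol 6.1.1.5.3 and 6.1.7.4 also move patients to survival follow-up once new anti-cancer therapy starts.
- Neither document gives a rule for assigning cause of death. SAP section 6 says that missing data are not imputed, and nothing says how a death of unknown cause would be classed.

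**The case against.** The strongest reply is that nothing is lost. Kaplan-Meier, log-rank and Cox come first in the paragraph, the Cox hazard ratio is the only one it names, and a SAP may add analyses to the protocol. The overall survival rows of SAP Table 2 are a median and survival rates, Figure 1C is an overall survival curve, and no table shell shows a Fine-Gray result. All of this stands. A second hazard ratio is implied by the method but not explicitly planned for display.

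The progression-free survival paragraph labels its Fine-Gray model a sensitivity analysis and the overall survival paragraph does not. A reader might infer that Fine-Gray has become the main survival analysis. The documents do not support that: the two paragraphs follow the same order, and the natural reading gives Fine-Gray the same secondary place in both. The label is a side issue in any case, since adding it would not remove the contradiction.

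A reader might also infer that cause of death goes uncollected in later follow-up. That is too strong. Disease status is followed in patients without progression, serious adverse event reporting separates non-progression deaths within its window, and the case report forms are not among the documents. What can be said is that the protocol and SAP state no rule.

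Finally, every hazard above is assumed. The 30% and 43% discordance figures need a four-fold and a six-fold excess of non-progression deaths, which nothing in the documents suggests. Even with equal hazards, small-sample noise gives opposite directions in 7.5% of trials.

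**Conclusion.** Wrong as written, and minor. The competing-event sentence contradicts the endpoint definition in both documents, and that conclusion needs no assumed numbers. The consequence is limited to a progression-related-death hazard ratio being misread as a survival result. Under a mild assumed imbalance the two large-sample ratios are 0.93 and 1.05, a gap far smaller than the uncertainty at 12 per arm. A nominally significant result in the contrary direction occurs in at most about 1.4% of trials in the scenarios tried. Overall survival is a secondary endpoint with no stated power or decision rule, and SAP Table 3 has a row for adverse events leading to death. It would be wrong to conclude that the trial has no valid overall survival analysis: the all-cause methods remain specified.

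**What to change.** In the overall survival paragraph of SAP 7.1, state that death from any cause is the event for Kaplan-Meier, log-rank and Cox, and that these results fill the overall survival rows of Table 2 and Figure 1C. Then do one of two things:

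- delete the competing-event and Fine-Gray sentences; or
- move them to a separately named supplementary analysis of progression-related death, with a rule for assigning cause of death that covers unknown cause.

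The cost is two or three SAP sentences. Deletion needs no new data, patients or visits. The cause-of-death rule is needed only if the supplementary analysis is kept.
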